#### STATISTICAL ANALYSIS:

We will use exploratory data analyses to review our data looking for extreme values which will be checked for transcription or other errors. Because our outcome measures will be measured multiple times, our intent is to use repeated measures ANOVA to compare outcome measures among treatment and control. However, as this is a pilot study designed to demonstrate proof of concept and to generate data with which to make accurate power calculations, we may initially analyze within-group changes using paired t-tests and among-group differences with independent samples t-tests.

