#### **TESTING PROCEDURES:**

\*Based on each subject's schedule and availability, the Principal Investigator or clinical investigative team may choose not to perform every research procedure described below. If this occurs it will be noted in the participant research notes. Participants may also be asked to repeat one or more of the research tests should it be necessary due to a technical error in its performance and/or measurement, an inadequate sample is obtained for analysis, or there was an unforeseen problem with data collection.

1. **Blood Sampling:** Blood plasma and/or serum will be used to measure cardio-metabolic and angiogenic factors (growth factors, inflammatory cytokines, cardio- metabolic risk factors, and markers of nutritional status). We may also measure endothelial progenitor cells, new hormones, inflammatory proteins and biomarkers as other technologies for measuring biomarkers of cardiovascular disease are identified. We will store plasma and serum and blood

cells for analysis at a later time. These samples will be de-identified. Genetic testing will also be performed on blood samples.

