2. Treadmill Exercise Test: The tests described below will be supervised by staff clinicians with the assistance of CPR-trained study team members. Subjects will walk on a treadmill at approximately 2mph and grade is increased every 2 minutes until the subject cannot continue. Subjects will wear a mask with a mouthpiece that will collect expired air for measurement of ventilated gasses. Subjects are instructed to report the onset of claudication pain and then to walk as long as they can endure the pain (at which time the test will end). Heart rate and ECG are monitored continuously; arm and ankle blood pressure is monitored intermittently throughout the protocol using either auscultation or Doppler ultrasound. Cardiac output (PhysioFlow Enduro) and calf muscle oxygen saturation (Oxiplex TS near-infrared spectroscopy) may also be non-invasively measured during the test. Exercise tests may be stopped if the subjects indicate they are unable to continue or they experience any of the following: chest pain, dizziness, faintness, fatigue, pallor, cyanosis, cardiac arrhythmias or decompensation, or severe hyper- or hypotension (American College of Sports Medicine 2006. Guidelines for Exercise Testing and Prescription 7th ed.). Subjects may be asked to repeat this test while wearing a NMES unit. During Phase 3 & 5 this test will be performed twice. Once to establish any improvements in how long the patient can walk they will be asked to walk as long as possible. The second test will be submaximal and will be terminated when the patient reaches the same time and grade completed in a previous research testing phase. The submaximal test will be supervised by a CPR-trained exercise physiologist.

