3. Strength Testing: A) Muscular strength (leg extension, leg press, and/or leg flexion) will be measured by 1-repetition maximum (1RM) testing on Keiser K-300 air powered machines or a Biodex strength testing system. Participants will complete a brief, low-intensity warm-up prior to the test. Participants will be asked to perform exercises against a gradually increasing resistance after each successful exercise repetition until the maximal load is obtained. They will be perform multiple trials (typically ~3-7) with ~ 1 minute of rest between trials. B) Plantar and dorsiflexion will be measured using a hand-held dynamometer or with the Biodex strength testing system. Participants will be properly stabilized to ensure minimal movement artifacts. Additionally, verbal encouragement will be provided during task to encourage maximal volitional contraction.

5. Functional Tests and Questionnaires: The physical performance tests include the Modified Physical Performance Test [standing balance, chair rise, book lift, put on and remove jacket, pick up a penny, turn 360 degrees, 50-foot walk, stair ascent/descent, self-selected gait speed (8-foot walk)], grip strength, balance, and the 6-minute walk. We will also administer questionnaires (attached) including the Walking Impairment Questionnaire (WIQ), SF-36, the Life Space Questionnaire, and the Vascular Quality of Life (VascuQoL). Participants may be asked to repeat these tests while participating in the intervention so that we may assess interim efficacy.

6. Body Composition: Total and regional fat mass, lean tissue mass, % body fat, bone mineral content, and bone density will be determined by dual-energy x-ray absorptiometry (DXA). Computed tomography scans of the abdomen and leg are done to quantify regional fat and muscle distribution. The DXA and CT scans are performed by radiology technicians. [\*DXA and CT scans will only be performed during post-revascularization testing (Phase 3) and 3-month testing (Phase 5).] We will also measure body circumferences with a tape measure.

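### The between-group analysis does not adjust for the Phase 3 value, although that value is collected for at least the treadmill and DXA/CT outcomes, so it will usually be less precise than it could be

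*Combined protocol and SAP*

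**What the plan says.** The STATISTICAL ANALYSIS section is one paragraph. For the comparison of groups it says "our intent is to use repeated measures ANOVA to compare outcome measures among treatment and control". Because the study is a pilot, it adds that "we may initially analyze within-group changes using paired t-tests and among-group differences with independent samples t-tests". One stated purpose of the pilot is "to generate data with which to make accurate power calculations".

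The paragraph names no covariate. It does not say which ANOVA term is tested (group main effect or group by time), which time points enter, or whether the independent t-tests use changes or Phase 5 values.

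TESTING PROCEDURES shows where a Phase 3 value will exist:

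- Item 2, Treadmill Exercise Test: "During Phase 3 & 5 this test will be performed twice".
- Item 6, Body Composition: "DXA and CT scans will only be performed during post-revascularization testing (Phase 3) and 3-month testing (Phase 5".
- Item 5, Functional Tests and Questionnaires, does not state the phases but allows interim measurements: "Participants may be asked to repeat these tests while participating in the intervention so that we may assess interim efficacy".

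The note that opens TESTING PROCEDURES says that the investigators "may choose not to perform every research procedure described below", so a Phase 3 value can be missing for some participants.

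**The concern.** For outcomes measured at both phases, the Phase 3 value is usually a strong predictor of the Phase 5 value. Using it as a covariate removes that part of the variance from the group comparison. The plan does not do this under any reading:

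- **Group-by-time interaction.** With two phases this is the change-score t-test. It is valid, but it fixes the slope on Phase 3 at 1 instead of estimating it.
- **t-test on Phase 5 alone.** This fixes the slope at 0, discards the Phase 3 data and leaves any chance Phase 3 difference in the estimate.
- **Group main effect.** This averages Phase 3, where no effect is expected, with Phase 5, and so halves the effect. The text does not say that this term is meant, but it does not exclude it.

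Two things are at stake. Intervals would usually be wider than necessary in a study that is probably small. The planned output would also not directly give the residual SD after Phase 3 adjustment, or the Phase 3 to Phase 5 correlation. A baseline-adjusted next trial is sized from one or the other.

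**Working it through.** The plan states no sample size, power or alpha, so there is no figure of its own to reproduce.

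**Assumptions (none is in the documents).** Two equal groups of n; equal SD at both phases, set to 1; correlation rho between Phase 3 and Phase 5; no expected Phase 3 difference between groups; Phase 3 measured before the intervention; two-sided 5% test.

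**Step 1: large-sample variance, relative to Phase 5-only = 1.**

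- Change score (group by time with two phases): 2(1 − rho)
- ANCOVA on Phase 3: 1 − rho²
- ANCOVA relative to change: (1 − rho²) / [2(1 − rho)] = (1 + rho)/2

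**Step 2: small-sample cost of estimating the slope.** Multiply the ANCOVA variance by (2n − 3)/(2n − 4). This is 17/16 = 1.06 at n = 10, 27/26 = 1.04 at n = 15 and 37/36 = 1.03 at n = 20.

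| rho | ANCOVA/change, large sample | same, n = 15 | ANCOVA/Phase 5-only, large sample | same, n = 15 |
|---|---|---|---|---|
| 0.5 | 0.75 | 0.78 | 0.75 | 0.78 |
| 0.7 | 0.85 | 0.88 | 0.51 | 0.53 |
| 0.8 | 0.90 | 0.93 | 0.36 | 0.37 |

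**Step 3: where ANCOVA stops helping.** It beats Phase 5-only when rho > sqrt(1/(2n − 3)), and change scores when rho < (2n − 5)/(2n − 3). Both hold for rho from 0.24 to 0.88 at n = 10, 0.19 to 0.93 at n = 15 and 0.16 to 0.95 at n = 20. Outside that range it gains nothing over the better alternative.

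**Step 4: power by simulation** (40,000 trials per cell, true difference 0.8 SD).

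| n per group | rho | ANCOVA | Change | Phase 5-only |
|---|---|---|---|---|
| 15 | 0.5 | 67% | 57% | 57% |
| 15 | 0.7 | 83% | 78% | 56% |
| 15 | 0.8 | 93% | 92% | 56% |

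Type I error was about 5% for all three methods (n = 15, rho 0.7). Two cells at n = 10 show no gain: at rho 0.2, 39% for ANCOVA against 39% for Phase 5-only; at rho 0.9, 96% for ANCOVA against 97% for change.

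**Step 5: if the group main effect were tested.** Averaging the two phases halves the effect, and the variance factor on the scale of the full effect is 2(1 + rho), or 3.4 at rho 0.7. By normal approximation with 20 per group and a 0.8 SD effect, power is 0.28, against 0.90 for change and 0.94 for ANCOVA.

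**Step 6: what the choice of SD does to the next trial.** Per-group size for a 0.5 SD effect at 80% power, from a two-sample t-test with SD multiplied by 1, sqrt(2(1 − rho)) or sqrt(1 − rho²), at rho 0.5/0.7/0.8:

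- Phase 5 SD: 64 throughout
- Change SD: 64/39/27
- Adjusted SD: 49/34/24

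**Step 7: skipped Phase 3 tests.** If a fraction m lack Phase 3, complete-case ANCOVA keeps (1 − m)/[(1 − m) + m(1 − rho²)] of the information in a model that retains those participants. With m = 0.2 and rho 0.5 this is 0.80/(0.80 + 0.15) = 0.84; at rho 0.7 and 0.8 it is 0.89 and 0.92.

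**Step 8: non-random allocation.** If the groups truly differ by D at Phase 3, the ANCOVA and change-score estimates differ by (1 − rho)D. With D = 0.5 SD this is 0.25/0.15/0.10 SD at rho 0.5/0.7/0.8, which is a difference in what is estimated and not only in precision.

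**The case against.** The strongest reply is that repeated measures ANOVA already uses Phase 3, because Phase 3 is one of the repeated values. If group by time is the tested term, the analysis is valid and the gain from ANCOVA shrinks as the correlation rises: at 15 per group it is 10 power points at rho 0.5, 5 at 0.7 and 1 at 0.8. The large losses belong to readings that the text permits but does not state; a comparison of changes is at least as natural a reading of the t-test sentence. This stands, and it limits the size of the point.

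Other parts of the reply also stand:

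- The effect of a chance Phase 3 imbalance is not a separate harm. A one-standard-error imbalance at n = 15 is sqrt(2/15) = 0.37 SD. At rho 0.5/0.7/0.8 it shifts the Phase 5-only estimate by 0.18/0.26/0.29 SD and the change estimate by −0.18/−0.11/−0.07 SD. On average this is the same loss that the variance ratios express.
- The correlation and adjusted SD can be recovered by algebra from the two phase SDs and the change SD. The planning information is not lost, only not directly reported.
- Plain ANCOVA is weak when Phase 3 is often missing. At rho 0.5 with 20% missing, its large-sample variance relative to Phase 5-only is 0.75/0.8 = 0.94. With 12 complete cases per group the factor 21/20 makes it about 0.98. This favours the mixed model.
- Randomization, the number of arms and the timing of Phase 3 relative to each intervention are not stated. The treadmill item also refers to an earlier testing phase, so the two-phase arithmetic fits DXA/CT most cleanly.

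None of this removes the point. Adjustment is more precise over most of the plausible range, and stating it would also settle which contrast is meant.

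**Conclusion.** The concern holds, as a loss of efficiency and not of validity. The plan names no baseline adjustment for outcomes whose Phase 3 value it will collect. Against the most favourable reading, group by time, adjustment would cut variance by about 7% to 22% at 15 per group for correlations from 0.8 down to 0.5. Against a Phase 5-only t-test it would cut variance by about 22% to 63% for correlations from 0.5 up to 0.8.

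These figures rest on assumed group size, correlation, equal SDs, two equal groups and a Phase 3 value taken before treatment. The pure precision argument also needs randomized allocation, which the documents do not state. Confidence is therefore medium. The change should be made because it is cheap and serves the pilot's own planning purpose, but the trial does not fail without it.

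**What to change.** In STATISTICAL ANALYSIS, for each outcome measured at both phases:

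- Make the between-group estimate the Phase 5 difference adjusted for the Phase 3 value of the same outcome, with a 95% CI, from ANCOVA or a baseline-adjusted mixed model.
- Prefer the mixed model where interim measurements exist or Phase 3 tests are skipped, so that those data and participants are kept. If allocation is randomized, Phase 3 can enter as a response with a common mean across groups.
- If all phases are modelled together, name the adjusted Phase 5 group contrast as the result, not the group main effect or the omnibus interaction.
- Report the residual SD and the Phase 3 to Phase 5 correlation for the next trial.
- State how participants are allocated. If allocation is not randomized, say that ANCOVA and change scores can estimate different quantities, do not assume a common Phase 3 mean, and give the change-score result as a sensitivity analysis.

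The cost is a wording change, one model per outcome and somewhat more analysis and reporting, with no new data. Each covariate uses one degree of freedom (variance factor 1.06, 1.04 or 1.03 at 10, 15 or 20 per group). With few patients and a very low or very high correlation there is no gain.

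### The proof-of-concept aim has no lead outcome, criterion or multiplicity rule, so with about 30 measures the supporting outcome could be chosen after the data are seen

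*Combined protocol and SAP*

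**What the plan says.** The STATISTICAL ANALYSIS section of the combined protocol and SAP is one paragraph. Its main plan is: "our intent is to use repeated measures ANOVA to compare outcome measures among treatment and control". It then gives two purposes. The first is that "this is a pilot study designed to demonstrate proof of concept"; the second is to supply data for later power calculations. For that reason, "we may initially analyze within-group changes using paired t-tests and among-group differences with independent samples t-tests". The outcomes are referred to only collectively: "Because our outcome measures will be measured multiple times". The section gives no significance level, sidedness, sample size, lead outcome, multiplicity rule or definition of proof of concept.

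TESTING PROCEDURES supplies the candidate outcomes: blood markers (item 1), treadmill test (item 2), strength (item 3), functional tests and questionnaires (item 5), body composition (item 6) and ultrasound (item 7). Item 5 alone lists four questionnaires: "the Walking Impairment Questionnaire (WIQ), SF-36, the Life Space Questionnaire, and the Vascular Quality of Life (VascuQoL").

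The set is not fixed in either direction. Item 1 allows further markers "as other technologies for measuring biomarkers of cardiovascular disease are identified". The note that opens the section lets the team omit procedures for a participant. Item 5 allows functional tests and questionnaires to be repeated during the intervention to look at interim efficacy, without saying how often.

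**The concern.** Proof of concept is a conclusion about whether the intervention works, so it needs a stated basis. Here every outcome gets the same tests and none is set apart to carry the conclusion. With many outcomes, some will probably differ by chance, and the plan leaves open which of them may be cited.

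Two things are at stake. First, a positive statement would be weak evidence if it rests on an outcome chosen because it reached significance. Second, the plan's other purpose is affected: an outcome selected for significance in a small sample has, on average, an exaggerated effect estimate, and powering the next trial on it would make that trial too small.

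The permitted within-group paired tests add to the problem. A change from Phase 3 (post-revascularization) to Phase 5 (3 months) within one arm cannot separate the intervention from recovery or repeated testing.

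**Working it through.** The documents give no error rate or sample size, so there is no stated figure to reproduce. The check asks how large the problem is under stated assumptions.

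**Number of outcomes (from TESTING PROCEDURES).** Treadmill 4 (walking time, claudication onset, expired gases, arm and ankle pressure), strength 5, functional 4 (performance test as one score, grip, balance, 6-minute walk), questionnaires 4, DXA 5, CT 2, circumferences 1, ultrasound 1, blood-marker classes 4.

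4 + 5 + 4 + 4 + 5 + 2 + 1 + 1 + 4 = 30.

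Adding the two optional treadmill measures (cardiac output, calf oxygen saturation) and counting total and regional fat separately gives 33. Scoring the nine performance items separately gives 33 − 1 + 9 = 41. A blood-marker class can hold several analytes.

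**Assumptions.** Significance level 0.05 per test, two-sided, no true effect on any outcome. None of these is in the documents, so each is varied below, apart from the null.

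**Independent outcomes.** P(at least one false positive) = 1 − (1 − α)^k.
- k = 30, α = 0.05: 1 − 0.95^30 = 78.5%; expected false positives 30 × 0.05 = 1.5
- k = 20: 1 − 0.95^20 = 64.2%
- k = 14: 1 − 0.95^14 = 51.2%
- k = 30, α = 0.01: 1 − 0.99^30 = 26.0%
- k = 30, α = 0.10: 1 − 0.90^30 = 95.8%
- k = 30, treatment-favouring results only (0.025 each): 1 − 0.975^30 = 53.2%

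**Equally correlated outcomes.** Each test statistic is √ρ·U + √(1 − ρ)·E, with U shared across outcomes. The probability is 1 minus the average over U of [Φ((1.96 − √ρU)/√(1 − ρ)) − Φ((−1.96 − √ρU)/√(1 − ρ))]^k. For treatment-favouring results only, the second Φ term is dropped.

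| Correlation | 30 outcomes, two-sided | 20 outcomes, two-sided | 30 outcomes, favouring treatment only |
|---|---|---|---|
| 0 | 78.5% | 64.2% | 53.2% |
| 0.1 | 76.6% | 62.6% | 46.4% |
| 0.3 | 66.2% | 54.0% | 35.0% |
| 0.5 | 50.7% | 41.9% | 25.5% |
| 0.6 | 42.2% | 35.4% | 21.1% |
| 0.7 | 33.9% | 28.9% | 16.9% |
| 0.8 | 25.6% | 22.4% | 12.8% |

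**Correlation by domain.** Thirty outcomes in seven domains, two-sided 0.05, 200,000 draws: 69.6% with correlation 0.5 within and 0.1 between domains; 59.9% with 0.7 and 0.2; 51.9% with 0.8 and 0.3.

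**Small-sample t-tests.** With 30 outcomes and an assumed 10 or 20 per arm (4,000 runs), between-group tests give about 78%, 66% and 52% at correlations 0, 0.3 and 0.5. With 20 outcomes and 15 per arm, simulation gives 43% at correlation 0.5, against 41.9% in the table. Adding paired tests in the treated arm, with 30 outcomes, raises the figures to about 92–93%, 84% and 71–72%.

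**With a remedy.** One lead outcome at 0.05 gives 5.0%. Bonferroni over 30 outcomes, at 0.05/30 = 0.00167 each, gives 4.9% if independent.

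**The case against.** The strongest reply is that the plan contains a gap, not a faulty rule. It sets no criterion for proof of concept. A reader might infer that any nominally significant result would be declared proof of concept, but the text never says so. The t-tests are only a possible first step, and the second purpose, data for power calculations, needs no significance claim. This stands, and it limits the point to what the plan leaves open. It does not remove it: repeated measures ANOVA handles several time points within one outcome and does nothing for multiplicity across outcomes. The power-calculation purpose is itself exposed if the outcome is selected for significance.

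A reader might also infer that a chance positive is more likely than not. The documents do not support that as a general statement. They give no significance level, sidedness or sample size, and the probability drops below one half under several plausible assumptions shown above.

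The count can be challenged too. Item headings describe procedures, some are optional, and not every measure need be a tested outcome. That is fair, although other ways of counting give more than 30. Finally, the text provided opens at the study procedures, so objectives may be stated in material not supplied. The finding is therefore about the text provided.

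**Conclusion.** The point stands as an omission with real consequences. In the text provided, a proof-of-concept aim is attached to about 30 undifferentiated outcomes and an open biomarker list, with no lead outcome, criterion or adjustment.

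At an assumed two-sided 0.05 with 30 outcomes and no true effect, the chance of at least one false-positive between-group result is 79% if independent, 66% at correlation 0.3 and 51% at 0.5. It is lower with higher correlation, fewer outcomes, a stricter level or one favourable direction, and higher with within-group tests. Every figure computed is well above 5%. In the two cases with a smaller per-test rate the comparison is starker still: 26% against 1% at the 0.01 level, and 12.8% to 53.2% against 2.5% for treatment-favouring results.

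Two limits apply. These probabilities assume that no outcome responds; if some do, selection is not purely by chance, though some inflation of the selected effect remains. That inflation is not quantified, because the documents give no sample size or variability. This should be corrected before analysis.

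**What to change.** Add to STATISTICAL ANALYSIS, before any outcome data are analysed:

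- Name one lead functional outcome already collected. Six-minute walk distance and maximal treadmill walking time are both candidates. Nothing in the text favours one over the other, so the choice is the investigators'.
- Name one treatment-versus-control contrast. INTERVENTIONS describes active training and NMES, and the analysis section speaks of "among-group differences with independent samples t-tests", so the arms in the contrast need stating.
- Base the proof-of-concept statement on the between-group difference at Phase 5 (3 months), adjusted for the Phase 3 (post-revascularization) value, and not on within-group paired tests. This takes Phase 3 as the value before the intervention; the text provided does not say when each intervention starts, so this should be confirmed.
- Label all other outcomes, including biomarkers added later and interim repeats, exploratory. Report them as estimates with confidence intervals that cannot by themselves support the claim.

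The cost is a few sentences, with no new measurements or participants. The small downside is giving up headline claims from secondary measures. Adjusting over all outcomes would also control the error rate, but at 0.00167 per test it is demanding for a pilot and needs a closed outcome list, which this plan does not have.

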**PI: [name].**

**NCT 02607046**

**Approval: March, 28, 2019**

## **Post-revascularization rehabilitation to improve function in Veterans with peripheral arterial disease (PAD)**

### STUDY PROCEDURES:

#### **INTERVENTIONS**

1. **Active Exercise Training:** All participants who are in the exercise program will exercise for approximately 3 months, 3 times per week at the Baltimore VA Medical Center Annex, or the VA Medical Center. These exercise sessions will be supervised by exercise physiologists or trained staff. The aerobic exercise training program will include a warm up followed by 30-45 minutes of cumulative walking on a treadmill or around a track. Individuals will initially begin walking for 10-15 minutes per exercise session (depending on tolerance) and will progress weekly until 30-45 minutes of cumulative walking has been achieved. For individuals who experience claudication pain, they will be asked to walk until the claudication pain reaches a 3 on a 0-4 scale (0= no pain, 1 = onset of pain, 2 = moderate pain, 3 = intense pain, and 4 = maximal pain) after which they will rest. They will then be asked to walk again. This pattern of intermittent walking will be continued until the prescribed number of minutes of walking is met. Subjects will also be asked to walk at home on days they do not perform supervised exercise. Participants may also participate in strength training (ST) during the same session. This will consist of training of the knee extensors, knee flexors, plantar flexors and dorsiflexors. Subjects will perform approximately 1-3 sets of 4-15 repetitions for each exercise as tolerated. Training may be performed on Keiser K-300 air powered machines utilizing pneumatic resistance (Leg Extension Machine, Leg Curl Machine, Leg Press Machine) or with resistance bands or tubes. Each session of ST will take approximately 15-30 minutes. Blood pressure and heart rate will be assessed before and after each session. If the participant has type 2 diabetes and is on medications that may result in hypoglycemia, we will monitor blood glucose levels before and after exercise.

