2. **Passive Exercise Training (NMES):** Neuromuscular electrical stimulation (NMES) will be used to electrically induce contraction of the plantarflexors and dorsiflexors of both lower extremities. The protocol will employ an FDA cleared device for this purpose. NMES is routinely used in clinical care and has been used in other studies at UMB. Our specific protocol will require the application of NMES units on each lower extremity. Electrodes will be placed over the plantar and dorsiflexors of each leg. The stimulator's parameters setting will be adjusted to elicit contraction while maintaining participant comfort. Stimulation will be provided for approximately 15-30 minutes daily as tolerated by the participant.

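### The initial paired t-tests allowed for proof of concept cannot show a rehabilitation effect after revascularization; that conclusion should rest on a baseline-adjusted between-group difference

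*Combined protocol and SAP*

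**What the plan says.** Under STATISTICAL ANALYSIS, the stated plan for repeated outcomes is a controlled comparison: "our intent is to use repeated measures ANOVA to compare outcome measures among treatment and control". The next sentence qualifies this. It gives the reason as "as this is a pilot study designed to demonstrate proof of concept and to generate data with which to make accurate power calculations" and concludes that "we may initially analyze within-group changes using paired t-tests and among-group differences with independent samples t-tests". Only the ANOVA is stated as an intent. Both kinds of t-test are optional.

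The section does not call the paired tests descriptive, and it does not say which result would carry a proof-of-concept conclusion. Nor does it say whether the independent samples t-test would use follow-up values or changes, or would take account of the starting value.

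Three items under TESTING PROCEDURES bear on what a within-group change would contain:

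- **Body Composition** labels Phase 3 as the post-revascularization testing and Phase 5 as the 3-month testing, and confines DXA and CT to those two phases.
- **Treadmill Exercise Test** says "During Phase 3 & 5 this test will be performed twice", and that the second, submaximal test is "terminated when the patient reaches the same time and grade completed in a previous research testing phase". Applied at Phase 3, this implies some testing before Phase 3.
- **Functional Tests and Questionnaires** allows repeats during the intervention to look at interim efficacy.

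**The concern.** A paired t-test asks whether one group's mean changed. It does not ask whether rehabilitation changed it. In this population the two questions can separate. A change measured from before Phase 3 could include what the revascularization itself did. A change from Phase 3 to Phase 5 could include recovery from the procedure, decline, or familiarity with the walking and performance tests.

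The plan links the paired tests to the proof-of-concept aim without limiting how they may be read. If a significant within-group change were taken as proof of concept, the pilot could support a rehabilitation effect that is not there or, if patients decline over the period, miss one that is. Comparing the arms by whether each paired test is significant would be no better, since that is not a test of the difference.

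The independent samples t-test does address the right contrast. As named, however, it makes no use of the Phase 3 value, so a small pilot would either carry chance baseline differences into the follow-up comparison or lose precision.

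**Working it through.** **Reproduction.** The documents give no sample size, alpha, SD, effect or drift for this analysis, so there is no figure of the plan's to reproduce. Everything below is illustration.

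**Assumptions.** 10, 15 or 20 per arm; two-sided 5% alpha; normal changes with SD of change = 1 in each arm. Drift *c* is mean change not due to rehabilitation, in SD of change.

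**1. Paired test, no rehabilitation effect.** Noncentral t, df = n − 1, noncentrality c√n. Example: n = 15, c = 0.3 gives 0.3 × √15 = 1.16 on 14 df with critical value 2.145; rejection 19.2%.

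| Drift c | n = 10 | n = 15 | n = 20 |
|---|---|---|---|
| 0 | 5.0% | 5.0% | 5.0% |
| 0.1 | 5.9% | 6.5% | 7.1% |
| 0.3 | 13.6% | 19.2% | 24.7% |
| 0.5 | 29.3% | 43.8% | 56.5% |

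**2. Between-group test of change, drift shared by both arms.** The drift cancels, the noncentrality is 0, and the rejection rate is 5% whatever c is.

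**3. Reading one arm's paired test against the other's.** With shared drift and no effect, the chance that the treated arm alone is significant is p(1 − p), where p is the entry in step 1. At c = 0.3 and n = 10: 0.136 × 0.864 = 11.8%. At c = 0.5 and n = 20: 0.565 × 0.435 = 24.6%.

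**4. Drift in the other direction.** True effect 0.5, shared drift −0.3, so the treated arm changes by 0.5 − 0.3 = 0.2. The paired test detects it in 8.8%, 11.2% and 13.6% of trials (n = 10, 15, 20). The between-group test (df = 2n − 2, noncentrality 0.5√(n/2)) detects it in 18.5%, 26.2% and 33.8%.

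**5. Limit of the remedy: drift in the treated arm only.** Noncentrality c√(n/2), no rehabilitation effect. The between-group test rejects in 5.5–6.1% (c = 0.1), 9.7–15.2% (c = 0.3) and 18.5–33.8% (c = 0.5). It is biased by the same amount as the paired comparison; the rates are lower only because its standard error is larger.

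**6. Cost in precision.** Half-width of the 95% CI: within group t(0.975, n − 1)/√n; between groups t(0.975, 2n − 2)√(2/n).

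| n per arm | Within group | Between groups |
|---|---|---|
| 10 | 2.262/√10 = 0.72 | 2.101 × √0.2 = 0.94 |
| 15 | 0.55 | 0.75 |
| 20 | 0.47 | 0.64 |

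These are before adjustment for the Phase 3 value.

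**7. Does the between-group mean give a more accurate effect size for sizing a later trial?** Root-mean-square error is √(1/n + c²) within group and √(2/n) between groups under shared drift. At n = 10, c = 0.1: √0.11 = 0.33 against √0.20 = 0.45. At n = 20, c = 0.1: 0.24 against 0.32. The two are equal at c = 1/√n, which is 0.32, 0.26 and 0.22 for n = 10, 15 and 20. For smaller drift the between-group mean is the noisier input, so no general gain in sizing can be claimed.

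**The case against.** The strongest defence is that the safeguard is already written down. The intended analysis is a treatment-versus-control ANOVA, the sentence at issue also names between-group t-tests, and the paired tests are doubly hedged as something the team may do initially. Nowhere do the documents say that a within-group p-value will count as evidence of effect. This stands, and it limits the point: the harm depends on how the optional tests are used. A reader might infer that the plan rests its efficacy claim on uncontrolled change. The text does not support that; it leaves the use open.

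A second objection is that the magnitudes are all assumed. That also stands. A reader might infer that favourable drift is expected after revascularization, but the documents give neither size nor sign, and with no drift the paired test keeps its 5% level.

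A third concerns the power-calculation aim. It is tempting to add that taking the effect size from the between-group estimate would make a later trial better sized. Step 7 shows that this fails as a general claim at pilot sample sizes when drift is small. The SD of change is a legitimate power input under either analysis.

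Finally, it might be inferred that the unnamed visits and the unstated link between treatment and the two interventions are errors in their own right. The pair of phases is fixed for DXA and CT, the phase schedule is absent from the supplied text, and pages were removed. These are at most missing detail and are not pressed here.

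What the defence does not answer is that the proof-of-concept aim is given as the reason for the initial tests, with nothing to stop a paired result from being read as meeting that aim.

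**Conclusion.** The point holds as a minor one. The plan allows simple t-tests as a first analysis for proof of concept in place of the intended ANOVA, and the paired test among them cannot separate rehabilitation from procedure, recovery or retest change. A baseline-adjusted between-group comparison is a better method at little cost.

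Under the assumed 10 to 20 per arm and two-sided 5% alpha, shared drift of 0.1, 0.3 or 0.5 SD of change raises the paired test's false-positive rate from 5% to 5.9–7.1%, 13.6–24.7% or 29.3–56.5%, while the between-group test of change stays at 5%. That advantage rests on both arms sharing the drift. The conclusion itself, that within-group significance is not evidence of a rehabilitation effect, does not depend on these figures.

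**What to change.** Amend STATISTICAL ANALYSIS along these lines:

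- Any proof-of-concept conclusion will rest on the between-group difference at Phase 5 adjusted for the Phase 3 value, or on the group-by-time term of the repeated measures ANOVA, with a 95% CI, for outcomes measured at both phases.
- This replaces the unadjusted independent samples t-test.
- Within-group changes will be reported only as mean, SD and 95% CI, and their p-values will not be used as evidence of effect.
- The SD of change may be used in later power calculations.

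The change is to wording only; no visit, test or intervention is affected. The sponsor would need to identify which outcomes are measured at both phases, bearing in mind that "the Principal Investigator or clinical investigative team may choose not to perform every research procedure described below". The price is a wider interval: about 0.94 against 0.72 SD of change at an assumed 10 per arm, and 0.64 against 0.47 at 20, before baseline adjustment. Drift confined to one arm, for example if only treated participants repeat tests during the intervention, would remain and should be acknowledged when the results are interpreted.
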